Infusion-site/pump safety will be assessed during clinical visits, and any significant finding from the assessment will be reported as an AE (see Section 6.5.4.1).

Hemolysis occurring in study subjects after sudden pegcetacoplan withdrawal has been observed in 2 patients with PNH. Abrupt discontinuation of pegcetacoplan treatment may render PNH red blood cells unprotected against complement activation, potentially resulting in hemolysis leading to severe anemia.

Whenever possible, the study medical monitor will be contacted before interrupting or discontinuing treatment with IMP.

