6.5.3.2 Transfusions

All the RBC transfusions performed during the study period from screening until end of the study will be recorded.

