For any AE, a diagnosis should be recorded rather than individual signs and symptoms or abnormal laboratory findings. However, if at the time of AE reporting a diagnosis is not available, each individual sign/symptom should be recorded. If a diagnosis is subsequently established, all previously reported AEs based on signs and symptoms should be removed and replaced by one AE report based on the single diagnosis, with a starting date that corresponds to the start date of the first symptom of the eventual diagnosis. This approach also applies to signs and symptoms of CAD worsening, which should be reported as “CAD worsening/progression” or similar (e.g., relapse, flare progression or exacerbation), as appropriate.

Procedures

Diagnostic and therapeutic noninvasive and invasive procedures, such as surgery, should not be reported as AEs. However, the medical condition for which the procedure was performed should be reported if it meets the definition of an AE. For example, an acute appendicitis that begins during the AE reporting period should be reported as the AE and the resulting appendectomy entered in the comments section of the eCRF.

Treatment-emergent adverse event

A treatment-emergent AE is any AE temporally associated with the use of study treatment, i.e., from study treatment initiation until 8 weeks after study treatment discontinuation.

Serious adverse event

An AE that meets one or more of the following criteria/outcomes is classified as serious:

- Results in death.
- Is life threatening (i.e., at immediate risk of death).
- Requires in-patient hospitalization or prolongation of existing hospitalization.
- Results in persistent or significant disability/incapacity.
- Is a congenital anomaly/birth defect (i.e., in an offspring to the study patient).
- Is a medically important AE.

Medically important AEs are events that may not result in death, be life threatening, or require hospitalization but may be considered serious when, based upon appropriate medical judgment, may jeopardize the patient or subject or may require medical or surgical intervention to prevent one of the outcomes listed above. Examples of such events are intensive treatment in an emergency room or at home for allergic bronchospasm, blood dyscrasias or convulsions that do not result in hospitalization or development of dependency or abuse.

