## 5.2 KEY DEFINITIONS AND CONVENTIONS

### 5.2.1 Baseline values

The baseline value for any parameter will be defined as the last measurement prior to dosing on Day 1 of Part A of the study. If there are both central and local laboratory results available from samples collected at the same date and time, the central laboratory result will be selected for baseline. Baseline values can be obtained during screening or at visit 2 (before first dose). For ePRO questionnaires (FACT-An, SF-12, and EQ-5D-5L), baseline is collected prior to dosing but there are no times collected. When these assessments are performed on the date of first dose, the assessment will be considered as pre-dose for identification of a baseline.

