#### **7.3.1 Number of PRBC transfusions from Week 5 to Week 24.**

The number of PRBC transfusions from Week 5 to Week 24 in each treatment group will be compared using a stratified Wilcoxon rank-sum test-p-value will be calculated. Crude rates of transfusions will be calculated for the double-blind period (Part A). Patients who withdraw from randomized treatment or receive prohibited medication before Week 24 will have the number of transfusions estimated from the duration that they were in the study until withdrawal or initiation of prohibited medication.

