### 7.6.1 Adverse events

Pretreatment AEs are those occurring between ICF signature and the first IMP administration. Treatment-emergent Adverse Events (TEAEs) are defined as those AEs that start on or after the first dose of IMP and up to 8 weeks after the last dose of study medication.

An overall summary table will summarize the following information by treatment group.

- Treatment-emergent adverse events (TEAEs)
- Serious adverse events (SAEs)
- Non-serious adverse events
- TEAEs leading to premature discontinuation of IMP.
- TEAEs leading to death
- Device related TEAEs
- TEAEs by severity

Separate tables will be presented with the following summaries:

- TEAEs of special interest will be summarized: infections (defined as any AE with SOC “Infections and Infestations”), and injection site reactions (from eCRF)
- Pretreatment AEs by PT
- TEAEs by SOC and PT, including incidence rates.
- TEAEs by PT, including incidence rates.
- Non-serious TEAEs by SOC and PT, including incidence rates.
- Non-serious TEAEs PT, including incidence rates.
- Treatment-emergent SAEs PT, including incidence rates.
- TEAEs leading to premature discontinuation of IMP by PT, including incidence rates.
- TEAEs related to the IMP by PT, including incidence rates.
- Treatment-emergent SAEs related to the IMP by PT, including incidence rates.
- TEAEs by severity (mild/moderate/severe) and PT, including incidence rates.
- TEAEs that were injection site reactions, by PT.

The time at risk per patient is defined as time from first dose of study drug to last dose of study drug + 56 days (treatment-emergent), or death, if earlier, for those patients without a respective TEAE. For patients with an TEAE, time at risk is defined as the time from first dose of study drug to TEAE start date. Exposure adjusted incidence rates will be calculated as (number of patients with AE/total person-years at risk)\*100.

All AE data will be presented in a listing and include at least onset date, duration, relationship to IMP, severity, action taken with IMP, treatment of event, and outcome.

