### **7.6.2 Laboratory data**

Laboratory data will be graded for severity using the CTCAE v5.0 and all results of grade  $\geq 3$  will be considered clinically meaningful.

A frequency table will be presented to summarize patients with CTCAE grading  $\geq 3$  from Baseline until 8 weeks after end of treatment for each laboratory parameter for hematology, chemistry, and urinalysis.

Concentrations below the lower limit of quantification (LLOQ) (e.g., <0.20) or upper limit of quantification (ULOQ) will be replaced with LLOQ (e.g., 0.20) or ULOQ in summary tables. In listings, the original value will be presented (e.g., “BLQ” or “<0.20”). When an imputation is made in a summary table, a footnote will be added with the imputation approach.

A summary table will be presented with descriptive statistics and change from baseline for all laboratory parameters. Baseline will be taken as the last measurement prior to the first dose of IMP. For urinalysis parameters that are categorical (e.g., “None”, “Trace”, “1+”), a categorical summary of urinalysis results may be created to complement quantitative results.

All laboratory data will be presented in a listing and values outside normal range values will be flagged.

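### Apart from an implied EOS laboratory row and listings, no planned summary separates AEs, Grade ≥3 results or transfusions after stopping pegcetacoplan from those on drug, or compares hemolysis markers with the last on-treatment value

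*SAP*

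**What the plan says.** **The risk.** Protocol 4.3 states: "Hemolysis occurring in study subjects after sudden pegcetacoplan withdrawal has been observed in 2 patients with PNH". It adds that abrupt stopping may expose PNH red cells to complement and cause severe anemia. It gives no figure for CAD.

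**What is collected.** Protocol 6.5.3.2: "All the RBC transfusions performed during the study period from screening until end of the study will be recorded". AEs are recorded to 8 weeks after last dose (Protocol 6.5.4.1.2). A set of symptoms is to be reported as one diagnosis, and "This approach also applies to signs and symptoms of CAD worsening" (Protocol 6.5.4.1.1), so a flare after stopping is an AE. Hematology and chemistry are drawn at EOS, 8 weeks ±7 days after treatment stops (Protocol Table 2 and its notes).

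**What is summarized.**
- AEs (SAP 7.6.1): one window, from first dose to 8 weeks after last dose. Person-time for event-free patients runs to last dose + 56 days, or death if earlier. "For patients with an TEAE, time at risk is defined as the time from first dose of study drug to TEAE start date". Events of special interest are infections and injection site reactions.
- Grade ≥3 laboratory results (SAP 7.6.2): one frequency table, "from Baseline until 8 weeks after end of treatment for each laboratory parameter for hematology, chemistry, and urinalysis".
- Laboratory change (SAP 7.6.2): "A summary table will be presented with descriptive statistics and change from baseline for all laboratory parameters". Under SAP 5.2.1, "The baseline value for any parameter will be defined as the last measurement prior to dosing on Day 1 of Part A of the study".
- Transfusions: avoidance (SAP 7.2.3), number (7.3.1) and units (7.3.4) all end at Week 24, and crude rates cover Part A only. Durability of response, which counted a later transfusion as loss of response, is dropped (7.4).
- Visits (SAP 5.2.3): summaries follow a visit list in which EOT and EOS are separate entries.

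**The concern.** The sponsor has described a safety signal tied to stopping the drug, and the trial records the events, transfusions and laboratory values that bear on it. The planned tables then merge the off-drug weeks with the treatment period, or end before patients stop. A reader of those tables could not say how many patients had CAD worsening or a transfusion after stopping, or how much of their Hb gain they lost.

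This has become more pressing. SAP 1.1 closes enrollment early and lets treatment continue only until 10 July 2024, so every patient still on drug stops by then. The same section keeps safety reporting unreduced. At stake is the description of a named risk; the primary and key secondary tests are not involved.

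**Working it through.** The plan gives no figure on this point, so there is none to reproduce. The check compares the windows, then shows by arithmetic what pooling can hide.

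**1. First-event rule (SAP 7.6.1).** The rate is patients with the event ÷ total person-years at risk × 100. A patient with the term on drug is counted once, and that patient's person-time ends at the first event. A second event of the same term after stopping changes neither numerator nor denominator. If it is serious and the earlier one was not, it enters the SAE table, again without an on-drug/off-drug split. A pooled count of X patients is therefore compatible with any post-stop count from 0 to X.

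**2. Share of time at risk after last dose, event-free patient.** 56 ÷ (treatment days + 56):
- 24 weeks: 56/(168+56) = 25.0%
- 48 weeks: 56/(336+56) = 14.3%
- 96 weeks: 56/(672+56) = 7.7%

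Pooling spreads a post-stop event over 224/56 = 4, 392/56 = 7 or 728/56 = 13 times the post-stop person-time.

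**3. Illustration.** Every input is assumed: 20 patients, 336 days on drug, 4 with a first CAD-worsening event at day 168, and 3 patients with an event 28 days after last dose.
- Pooled, the 3 among the 4: 4/[(4×168 + 16×392)/365.25] × 100 = 21.0 per 100 person-years, 4 of 20 patients. This is identical to having no post-stop event.
- Pooled, the 3 in other patients: 7/[(4×168 + 3×364 + 13×392)/365.25] × 100 = 37.3, 7 of 20 patients.
- Split, on drug: 4/[(4×168 + 16×336)/365.25] × 100 = 24.2.
- Split, after stopping: 3/[(3×28 + 17×56)/365.25] × 100 = 105.8, whichever patients have the 3 events.

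With the 3 events in other patients, 0 to 4 patients with an on-drug event and 24 to 96 weeks of treatment, the post-stop rate is 1.6 to 14.0 times the pooled rate.

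**4. Laboratory reference.** A patient whose Hb rises by 1.5 g/dL (the response threshold) and falls back to the starting value shows an EOS change of 0 from Baseline but −1.5 from the last on-treatment value. The EOS row gives mean, quartiles and range (SAP 5.1), not a count of patients. If EOS change were normal with mean +0.5 g/dL and SD 1.0 to 1.5 (assumed), the share below Baseline would be Φ(−0.5/1.0) = 30.9% to Φ(−0.5/1.5) = 36.9%, or about 6 to 7 of 20 patients under a positive mean.

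**5. Timing.** EOS falls on Days 56 ± 7 = 49 to 63 after stopping. Of those 15 days, 7 (Days 57 to 63) lie past the 8-week limit of the Grade ≥3 table, if that limit is applied strictly. For a last dose on 10 July 2024, EOS falls between 28 August and 11 September 2024.

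**The case against.** The strongest reply is that the plan is not silent. SAP 7.6.2 does not say that its table is by visit, but SAP 5.2.3 makes the visit list the general rule and EOS is on it. A row of off-drug Hb, ARC, LDH, haptoglobin and bilirubin is therefore a fair inference. SAP 5.1 also commits to listing all collected patient data. With enrollment cut short, post-stop events could be counted by hand. This stands: a reader might infer that the plan shows nothing about hemolysis after stopping, or that the information is lost, and the documents support neither. What remains is that the row uses the pre-treatment reference and counts no event or transfusion, and that a listing is not a summary. The procedures table in SAP 6.4.2 might include transfusions, but it does not name them or split them at last dose.

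Second, the risk is documented in PNH, with a PNH-specific mechanism. It is not a trial objective, a safety endpoint or an event of special interest. The protocol itself sets safety endpoints to 8 weeks after EOT, and the SAP follows. This also stands: the documents do not show that withdrawal hemolysis occurs in CAD, or that the SAP departs from the protocol. Protocol 8.3.5 does separate the double-blind from the open-label period, but that split is not at last dose.

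Third, EOS need not be the only off-drug laboratory visit. Protocol 6.3.3.1 asks patients who stop treatment to continue their study visits, so some may be sampled earlier. Their off-drug values could then fall into ordinary visit rows, which is a further reason to separate them.

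Finally, the rates above come from assumed counts. They show how pooling behaves, not what happened in this trial. The splits could also be added in the table specifications that SAP 10.1 places after the SAP, which are not among the documents.

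**Conclusion.** The point holds as a cheap improvement to safety reporting. The existing tables do what the protocol asks. They do not separate AEs, Grade ≥3 results or transfusions after stopping from those on drug, and they never compare hemolysis markers with the last on-treatment value. The first-event rule can hide a post-stop flare from a term's count and rate completely. The dilution factors of 4 to 13 follow from the windows alone. The rates of 21.0, 37.3 and 105.8 per 100 person-years, and the 31% to 37% of patients below Baseline, rest on assumptions. No document gives a CAD withdrawal rate, so the real size is unknown. Nothing here touches the efficacy conclusions.

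**What to change.** For patients who received pegcetacoplan, keep the existing tables and add:

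- **(a) SAP 7.6.1.** Summarize TEAEs, SAEs and transfusions separately for time on pegcetacoplan and for the 56 days after last dose, each with its own time at risk. Count a post-stop event even if the same term occurred earlier.
- **(b) SAP 7.6.2.** Summarize Hb, ARC, LDH, haptoglobin and indirect bilirubin at EOS as paired change from the last value drawn on treatment, as well as from Baseline. Take that value from whichever visit supplied it: Table 2 as extracted marks no hematology or chemistry at EOT/ET, while Table 6 does, so the rule should not depend on that visit. Keep off-drug values of early stoppers still in follow-up out of the on-treatment reference.
- **(c)** Count patients with Hb below Baseline at EOS, and patients transfused after stopping.

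The cost is SAP wording and a few descriptive tables, with no new visits or samples. The drawback is small numbers and sparse off-drug laboratory sampling. The SAP should say that these tables describe the risk but cannot rule it out. A brief early hemolytic episode may show only in the AE and transfusion records.

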### **7.6.3 ECG data**

A frequency table will be presented to summarize the normal, abnormal but not clinically significant, and abnormal clinically significant ECGs recorded at each visit.

All ECG data will be presented in a listing.

### **7.6.4 Vital sign data**

Vital signs will be graded for severity using the CTCAE v5.0 and all results of grade  $\geq 3$  will be considered clinically meaningful. A frequency table will be presented to summarize the clinically meaningful abnormalities as recorded from treatment start date until 8 weeks after end of treatment for each parameter.

A summary table will be presented with descriptive statistics and change from baseline for all parameters.

All vital sign data including the overall interpretation (normal and if abnormal CS/NCS, Not Evaluable / Not done, etc.) as assessed by the will be presented in a listing. Reference ranges for heart rate, respiratory rate, blood pressure and body temperature will be added and values will be flagged as High/Low according to the reference ranges.

### 7.6.5 Immunogenicity data

Frequency tables will be presented to summarize the presence of anti-drug antibodies (ADA) to polyethylene glycol and to pegcetacoplan peptide. ADA evaluable patients are defined as:

- For baseline ADA: having at least one evaluable ADA sample at baseline.
- For treatment-emergent ADA and treatment-boosted ADA: having at least one evaluable ADA sample at baseline and at least one evaluable post dose sample.

Baseline ADA prevalence is defined as the number of patients with ADA positive at baseline divided by the number of patients with evaluable ADA at baseline.

Post-baseline ADA incidence is defined as the proportion of patients developing treatment-emergent ADA among those negative for ADA at baseline, or treatment-boosted ADA, among those positive for ADA at baseline.

Treatment-emergent ADA is defined as ADA that are present at a post-dose visit in a patient who had negative ADA at baseline.

Transient treatment-emergent ADA is defined as treatment emergent ADA detected in a single post dose sample (that was not the last assessment) or in more than 1 ADA sample where the first post dose and last ADA positive samples were separated by a period of less than 112 days (16 weeks), irrespective of any negative and positive samples in between. Persistent treatment emergent ADA is defined as more than 1 positive post dose ADA sample  $\geq 112$  days (16 weeks) apart or a positive ADA sample at the last time point with no further results available.

Treatment-emergent ADA can only be defined if baseline ADA result is obtained.

Treatment-boosted ADA is defined as positive ADA at a titer more than 4-fold the baseline titer found in a patient with positive ADA at baseline. Treatment-boosted ADA can only be defined if baseline ADA titer result is obtained.

Testing for neutralizing antibodies will be performed for all samples with positive ADA. Definitions for baseline Nab prevalence, post-baseline Nab incidence, and treatment-emergent Nab are the same as for ADA but with Nab.

A summary table of baseline ADA prevalence, post-baseline ADA incidence, treatment-emergent/boosted ADA, maximum titers for patients with treatment-emergent/boosted ADA,

time to treatment-emergent/boosted ADA, duration of treatment-emergent ADA, the proportion of patients with transient and persistent treatment-emergent ADA, baseline Nab prevalence, post-baseline Nab incidence, and prevalence of treatment-emergent/boosted Nab will be presented for pegcetacoplan peptide and polyethylene glycol.

Spaghetti plots of individual ADA titers will be presented for pegcetacoplan peptide and polyethylene glycol in semi-logarithmic format. Negative ADA results will be imputed as 0.1 to display on the log-scale.

All immunogenicity data will be presented in a listing.

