^a Open-label maintenance for a maximum of 48 weeks or until the product becomes commercially available, whichever occurs first. In the event that the commercial product is not yet available at the end of Part C, patients will be managed outside of the current study on a case-by-case basis, in accordance with applicable laws and regulations.

^b If needed and after consultation with the medical monitor, the screening period may be extended by up to 2 additional weeks.

Schedule of assessments

Table 1 **Schedule of assessments: Screening to Week 24 – Part A**

Study Period	Screening ^a	Part A: Double-blind treatment period									
		0	1	2	4	8	12	16	20	24	
Study Week	-4 (-6) to -1 ^a	0	1	2	4	8	12	16	20	24	
Study Day	-28 (-42) to -1 ^a	1	8	15	29	57	85	113	141	169	
Study Visit	1	2	3	4	5	6	7	8	9	10	
Visit window (\pm days)	0	0	2	2	7	7	7	7	7	7	
Informed consent	X										
Demographics	X										
Medical history	X										
RBC transfusions collection	X	X	X	X	X	X	X	X	X	X	
Inclusion/Exclusion criteria	X	X									
Randomization		X ^v									
Vaccination ^b	X			X			X				
Prophylactic antibiotic administration ^c	According to local standard practices in patients who cannot be vaccinated										
Full physical examination ^d	X	X								X	
Brief physical examination ^e			X	X	X	X	X	X	X		
Weight and height ^f	X	X	X	X	X	X	X	X	X	X	
12-lead ECG (prior to venipuncture)	X	X								X	
IMP administration ^g		Twice weekly-----→									
Infusion-site assessment ^h		X	X	X	X	X	X	X	X	X	
Concomitant medications/treatments	X	X	X	X	X	X	X	X	X	X	
Vital sign measurements ⁱ	X	X	X	X	X	X	X	X	X	X	
Urine studies	X				X	X	X	X	X	X	

Table 1 Schedule of assessments: Screening to Week 24 – Part A

Study Period	Screening ^a	Part A: Double-blind treatment period								
Study Week	-4 (-6) to -1 ^a	0	1	2	4	8	12	16	20	24
Study Day	-28 (-42) to -1 ^a	1	8	15	29	57	85	113	141	169
Study Visit	1	2	3	4	5	6	7	8	9	10
Visit window (± days)	0	0	2	2	7	7	7	7	7	7
Blood ^k										
Pharmacokinetics ^m		X	X	X	X	X	X			X
Anti-pegcetacoplan peptide and anti-PEG Ab assay ⁿ		X		X	X	X	X			X
Hematology	X	X ^w	X	X	X	X	X	X	X	X
Serum chemistry	X	X ^x	X	X	X	X	X	X	X	X
Coagulation profile ^o	X		X	X	X	X	X	X	X	X
TNF α , IL-6, IL-10, IFN γ and IL-1 β		X	X	X	X	X	X	X	X	X
Complement profile (C3, functional assays for classical and alternative complement pathways)		X	X	X	X	X	X	X	X	X
Flow cytometry for C3 deposition on RBCs ^p	X						X			X
Vitamin B ₁₂ /folate	X ^t						X			X
Iron/ferritin	X		X	X	X	X	X	X	X	X

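### The SAP's transient and persistent ADA definitions overlap: positives spanning under 112 days that include the last available sample meet both

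*SAP*

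**What the plan says.** SAP 7.6.5 starts from treatment-emergent ADA, defined as "ADA that are present at a post-dose visit in a patient who had negative ADA at baseline". It then gives each of two classes two alternative limbs.

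- Transient, one positive: "detected in a single post dose sample (that was not the last assessment".
- Transient, more than one positive: the first and last positives are "separated by a period of less than 112 days (16 weeks), irrespective of any negative and positive samples in between".
- Persistent, more than one positive: positive samples at least 112 days apart.
- Persistent, end of follow-up: "a positive ADA sample at the last time point with no further results available".

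The same section plans a summary table with the proportion of patients in each class, for both the pegcetacoplan peptide and polyethylene glycol. SAP 1.1 keeps the safety summaries as planned despite the early stop to enrollment, so this table is still due.

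**The concern.** The exclusion of the last assessment is attached only to the single-positive limb of transient. The multiple-positive limb looks at the span and nothing else. The phrase "irrespective of any negative and positive samples in between" concerns samples lying between the first and last positive, so it does not say what happens when the last positive is also the last sample. The second persistent limb captures any positive last sample, whatever came before. Nothing in 7.6.5 says that the classes are exclusive or which one wins.

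At stake is one descriptive summary of a protocol safety endpoint. A patient in both classes is counted twice, so the two proportions no longer partition the treatment-emergent patients.

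**Working it through.** **Inputs.** The cut-off is 112 days, stated as 16 weeks: 16 × 7 = 112, which agrees. Protocol Table 1 schedules the ADA assay in Part A at Weeks 0, 2, 4, 8, 12 and 24, with none at Weeks 16 or 20. Post-dose target days are 15, 29, 57, 85 and 169. The visit window is ±7 days from Week 4 on. Table 2 adds samples at Weeks 32, 40, 48, 56, 72, 96 (end of treatment) and 104 (end of study).

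**Part A patterns at nominal days.** Five post-dose samples give 2^5 − 1 = 31 patterns with at least one positive in a baseline-negative patient.

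| Pattern | Number | Span of positives | Transient | Persistent |
|---|---|---|---|---|
| Day 169 negative | 2^4 − 1 = 15 | at most 85 − 15 = 70 | yes | no |
| Day 169 positive, first positive Day 15 | 8 | 154 | no | yes |
| Day 169 positive, first positive Day 29 | 4 | 140 | no | yes |
| Day 169 positive, first positive Day 57 | 2 | 112 | no | yes |
| Days 85 and 169 only | 1 | 84 | **yes** | **yes** |
| Day 169 only | 1 | single sample | no | yes |

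The totals are 15 transient only, 8 + 4 + 2 + 1 = 15 persistent only, and 1 in both. No pattern falls in neither class. Counted as the SAP would count them, 16 transient + 16 persistent = 32 for 31 patterns. In general, if k patients meet both definitions, the two counts exceed the treatment-emergent total by k.

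**Visit windows.**
- Week 12 to Week 24: (169 − 7) − (85 + 7) = 70 to (169 + 7) − (85 − 7) = 98 days. Always under 112, so this pattern always overlaps within protocol windows.
- Week 8 to Week 24: (169 − 7) − (57 + 7) = 98 to (169 + 7) − (57 − 7) = 126 days. The two patterns first positive at Week 8 and positive at Week 24 overlap whenever the actual gap is under 112.
- Week 4 to Week 24: at least (169 − 7) − (29 + 7) = 126 days. Never overlaps.

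At most 1 + 2 = 3 of the 31 patterns can therefore overlap within protocol windows.

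**When later samples exist.** A patient positive at Weeks 12 and 24 who is positive again at Week 32 has a span of 225 − 85 = 140 days and is persistent only. If Week 32 is negative and no later positive follows, the patient is transient only. The overlap then moves to the end of the series: at nominal days, Weeks 40 and 48 for data through Week 48 (337 − 281 = 56 days), and Weeks 96 and 104 for the full schedule (729 − 673 = 56 days).

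**With the repair.** Requiring a negative last sample in the multiple-positive transient limb gives 15 transient, 16 persistent and 0 both in Part A. There is likewise no overlap through Week 48 or on the full schedule.

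**The case against.** The best defence is that the limbs are meant to be read in pairs: one positive is transient unless it is the last sample, in which case it is persistent; several positives are transient under 112 days and persistent from 112 days. On that reading the Part A patterns split 16 transient, 15 persistent and none in both, and the patient positive at Weeks 12 and 24 is transient.

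This needs the word 'single' in the second persistent limb, and the SAP does not have it. It also gives an odd ordering: a lone positive at Week 24 would be persistent, while positives at both Week 12 and Week 24 would be transient, so more evidence of persistence earns the weaker label. The reading shows that the authors may have intended exclusive classes. It does not make the text say so.

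Other parts of the defence stand.

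- A reader might infer that every patient positive at Weeks 12 and 24 is double-classified. That is so only if the baseline sample is negative, Week 12 is the first positive and no later result is available. Later samples are scheduled, and Protocol 6.5.4.3 follows patients positive in the last dosed sample every 6 months.
- A reader might infer that early termination makes the overlap more common. The documents do not show this. Under SAP 1.1 treated patients could continue to 10 July 2024, 182 days after enrollment stopped. Protocol Table 2 schedules an ADA sample at the end-of-study visit 8 weeks after discontinuation.
- A reader might infer that programmers would choose a class after seeing the data. SAP 10.1 has the dataset specifications written, reviewed and approved, SAP 10.2 requires independent double programming, and Protocol 6.4.9.1 blinds sponsor and investigators to both antibody results through the Week 24 analysis. Nothing shows the choice being made with unblinded results in hand.

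**Conclusion.** SAP 7.6.5 is wrong as written: it allows one patient to be both transient and persistent. At nominal days in a Part A report the overlap is the single Week 12 plus Week 24 pattern, rising to at most three patterns when the Week 8 to Week 24 gap falls below 112 days within visit windows. In later data cuts it sits at the final samples.

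This rests on a literal reading of the four limbs, a negative baseline sample, and no result after the last positive. The Part A figures also assume a report with data cut at Week 24, as Protocol 8.3.5 and SAP 7.6 describe. Patterns are not patients: the documents give no expected ADA incidence, so the number affected cannot be estimated.

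The consequence is minor: two descriptive proportions may add to more than the treatment-emergent total. Treatment-emergent incidence is unaffected, and all immunogenicity data are listed, so a reader could reclassify. It would go too far to say that the transient share is overstated as a matter of fact, because the documents do not state which class was intended for these patients.

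**What to change.** In SAP 7.6.5, add to the multiple-sample limb of transient: 'and the last available sample is negative'. Stating that persistent takes precedence over transient is equivalent. Either extends to both limbs the exclusion that the single-sample limb already uses, and makes the classes mutually exclusive. If the sponsor intended the paired reading, inserting 'single' in the second persistent limb would also separate them, but with the inconsistent ordering described above.

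The cost is one clause in the SAP and the matching line in the dataset specification. No new data, visits or analyses are needed.
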